5.0 DOSE MODIFICATIONS FOR TOXICITY

For patients who are unable to tolerate the protocol-specified dosing schedule, dose adjustments are permitted in order to keep the patient on study drug. If administration of Pegylated interferon must be interrupted because of unacceptable toxicity, drug dosing will be interrupted or modified according to rules described below. Toxicity will be assessed using the NIH-NCI Common Terminology Criteria for Adverse Events, version 5.0

https://ctep.cancer.gov/protocoldevelopment/electronic_applications/docs/CTCAE_v5_Quick_Reference_5x7.pdf

Pegylated interferon dose level modification guidelines

Patients who experience significant toxicity as listed in section 5.0 will have the dose reduced by 25% of the dose on subsequent cycles. Two dose reductions are allowed, as long as there is no evidence of progressive disease (see section 10.4) Patients who again experience dose modifying toxicity after 2 dose reductions will be taken off protocol therapy.

Dose Modification for Toxicity	Dose and schedule
Standard dose	1mcg/kg/dose
Dose Modifications	First Dose Modification: reduction by 25% of dose
	Second Dose Modification: reduction by 50% of dose
	Permanently discontinue if unable to tolerate second dose modification

*For patients whose weight is greater than 150kg, the maximum dose of Pegylated interferon to be administered is 150mcg/dose/week. (See table above)

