5.1 Non-hematological Toxicities

The dose of Pegylated interferon will be reduced for any of the following toxicities at least possibly attributed to Pegylated interferon

- Any Grade 4 non-hematological toxicity
- Any Grade 3 non-hematological toxicity with the specific exclusion of:

- Grade 3 nausea and vomiting controlled by antiemetics
- Grade 3 fever or infection
- Grade 3 fever, myalgias, arthralgias, and rigors.
- Grade 3 hypophosphatemia, hypokalemia, hypocalcemia or hypomagnesemia responsive to oral supplementation.

- Any Grade 2 non-hematologic toxicity that persists for > 3 days and is considered sufficiently medically significant or sufficiently intolerable by patients that it requires treatment interruption
- Any other adverse event attributed to Pegylated interferon that requires treatment interruption for > 3 days or which recurs upon drug re-challenge and requires treatment interruption.
- Non-hematological toxicity that causes a delay of more than 14 days between treatment cycles.

Patients who experience non-hematologic toxicity should have appropriate laboratory testing at least weekly until the toxicity has resolved.

If the toxicity does not return to less or equal than Grade 1 within **14** days, the patient will no longer be eligible to receive treatment on this study.

If the toxicity returns to less or equal to Grade 1 within 14 days, the patient may restart the study drug at initial dose modification once weekly and remain at that dose.

If the same Grade 3 or 4 non-hematologic toxicity recurs, hold drug and wait until toxicity returns to less or equal to Grade 1. If toxicity returns to less or equal to grade 1 within 14 days, the patient may restart the study drug at second dose modification and remain at that dose. If the toxicity does not return to less than Grade 1 within **14** days, the patient will no longer be eligible to receive treatment on this study.

If the same Grade 3 or 4 non-hematological toxicity recurs and it is felt to be due to the study drug, the patient will no longer be eligible to receive pegylated interferon alfa-2b.

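### Section 5.1 gives two incompatible recovery limits after a recurrent Grade 3 or 4 non-hematologic toxicity, and Section 5.0 does not say from which dose its 25% and 50% reductions are taken

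*Combined protocol and SAP*

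**What the plan says.** **Recovery after toxicity (Section 5.1).** For a first occurrence, a patient whose toxicity falls to Grade 1 or lower within 14 days may restart at the first dose modification. The companion sentence, which begins "If the toxicity does not return to less or equal than Grade 1 within" 14 days, ends treatment.

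For a recurrence of the same Grade 3 or 4 toxicity, the drug is held until the toxicity is Grade 1 or lower. Then: "If toxicity returns to less or equal to grade 1 within 14 days, the patient may restart the study drug at second dose modification". The removal sentence that follows begins "If the toxicity does not return to less than Grade 1 within" 14 days. A closing sentence begins "If the same Grade 3 or 4 non-hematological toxicity recurs and it is felt to be due to the study drug" and ends the drug, without saying which recurrence it means.

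**Size of the reductions (Section 5.0).** The text says patients with significant toxicity "will have the dose reduced by 25% of the dose on subsequent cycles", and adds: "Two dose reductions are allowed, as long as there is no evidence of progressive disease". The table beneath starts from a standard dose of 1 mcg/kg and lists "First Dose Modification: reduction by 25% of dose" and then "Second Dose Modification: reduction by 50% of dose". Neither says whether the percentage is of the standard dose or of the dose the patient is then receiving.

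**Where this feeds in.** Section 9.6 defines a toxic event as a patient who has had two dose reductions and then another significant toxicity. It calls for a review at 2 of 9 or 4 of 17.

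**The concern.** The restart and removal sentences should divide patients cleanly: whoever may not restart comes off, and nobody falls under both. After a recurrence they overlap, so two physicians who each follow the protocol to the letter could continue or remove the same child.

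The consequence goes beyond individual care. The toxicity monitoring counts only patients who have reached two reductions, and the disputed sentence decides whether some patients ever get that far. With 9 and then 17 patients, the count is small enough for a single classification to matter.

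The dose levels raise a lesser concern. Without a stated base, the second level can be computed in more than one way, and patients of the same weight could receive different doses under the same label.

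**Working it through.** **1. Recovery limits, by grade reached within 14 days (Section 5.1)**

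| Grade | First occurrence: restart sentence | First occurrence: removal sentence | Recurrence: restart sentence | Recurrence: removal sentence |
|---|---|---|---|---|
| 0 | may restart | not removed | may restart | not removed |
| 1 | may restart | not removed | **may restart** | **removed** |
| 2 or more | no restart | removed | no restart | removed |

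The first-occurrence columns agree in every row. The recurrence columns disagree in one row only, Grade 1. Section 5.2 (hematologic toxicity) has no such pair of sentences and is not affected.

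**2. Consequence for the Section 9.6 count**

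Follow a patient through the 5.1 sequence, assuming no other dose reductions:

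- First toxicity, recovery, restart at the first modification: 1 reduction.
- The same toxicity recurs, and the patient is at Grade 1 within 14 days.
 - Removal sentence applied: the patient leaves with 1 reduction. Since 1 < 2, this patient can never be a toxic event.
 - Restart sentence applied: 1 + 1 = 2 reductions. Another significant toxicity then makes the patient a toxic event.

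The triggers are 2 of 9 and 4 of 17. If one event has already been counted among the first 9, or three among 17, how this one patient is handled can decide whether the review takes place.

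**3. Second dose level (Section 5.0)**

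Inputs: standard dose 1 mcg/kg; text, 25% per reduction with two allowed; table, 25% and then 50%.

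The table's own figure comes first. Two steps of 25% of the standard dose give 1 − 0.25 − 0.25 = 0.50 mcg/kg, a 50% total reduction. This reproduces the table.

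The other readings that the wording allows are:

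- Text, 25% of the current dose twice: 0.75 × 0.75 = 0.5625 mcg/kg (56% of standard).
- Table, 50% of the current dose: 0.75 × 0.50 = 0.375 mcg/kg (37.5% of standard).

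Highest over lowest: 0.5625 / 0.375 = 1.5.

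Section 4.3 rounds the calculated dose up to the next 5 mcg. With illustrative weights:

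| Weight | 0.5625 mcg/kg | 0.50 mcg/kg | 0.375 mcg/kg |
|---|---|---|---|
| 20 kg | 11.25 → 15 mcg | 10 → 10 mcg | 7.5 → 10 mcg |
| 40 kg | 22.5 → 25 mcg | 20 → 20 mcg | 15 → 15 mcg |
| 60 kg | 33.75 → 35 mcg | 30 → 30 mcg | 22.5 → 25 mcg |

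At 20 kg the first modification is 0.75 × 20 = 15 mcg. Under the compounded reading, the second modification would therefore leave the given dose unchanged.

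**The case against.** **Section 5.0 contradicts itself.** A reader might infer this from a text that says 25% each time and a table that says 50%. The documents do not support it. If both percentages are taken from the standard dose, which heads the table, text and table give the same 0.50 mcg/kg. What stands is that the base is not stated.

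**The size of the second step alters the Section 9.6 count.** The definition counts how many reductions a patient has had, not how large they were. Any effect of size would be indirect, through later toxicity, and the documents give nothing from which to estimate it. Only the recovery sentences bear directly on the count.

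**The primary endpoint is compromised.** The responder definition and the two-stage decision rule use neither the dose level nor the recovery grade. Under Section 9.4, a patient who stops before the first response evaluation counts as a non-responder, so a very early removal could matter. That is a possible side effect and not a defect in the endpoint.

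**The recovery conflict is a slip in one sentence.** It is narrow: one grade, one sentence, and recurrence of the same toxicity only. The Grade 1 or lower wording also appears twice in the same paragraph. On the other side, the restart sentence is permissive while the removal sentence is mandatory, so a physician could fairly treat removal as governing. These cues point in different directions, and no other section settles the matter. Nor does the closing sentence on recurrence: if it covered the first recurrence, it would cancel the restart at the second modification for any toxicity felt to be due to the drug.

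**The physicians involved may share a reading.** They may, so the claim is only that patients could be handled differently.

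**Conclusion.** The recovery rule after a recurrence is wrong as written. A patient at exactly Grade 1 is both allowed to restart and required to stop, and the documents do not resolve it. The extent is limited to recurrence of the same Grade 3 or 4 non-hematologic toxicity. Its importance comes from governing restart or removal and from deciding who can reach the two reductions needed for a Section 9.6 toxic event, against triggers of 2/9 and 4/17. This assumes that the patient's only earlier reduction was for the same toxicity. The documents do not say how many patients to expect in this position, so no effect on the probability of a review can be given.

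The dose half is an undefined term and not a contradiction. Readings of the second level run from 37.5% to 56% of standard, with 50% the one on which text and table agree. The difference in the dose actually given depends on weight, because of rounding.

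**What to change.** - **Section 5.1:** reconcile the restart and removal sentences after a recurrence to a single recovery limit, so that every grade leads to one outcome. In the same edit, say which recurrence the closing sentence refers to.
- **Section 5.0:** reconcile the text and the table by stating the reference dose for each modification level.
- **Section 9.6:** once 5.1 is settled, check that the toxic-event definition counts the intended patients, including any removed after one reduction.

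Which recovery grade and which dose levels apply is for the sponsor to decide; none is proposed here. The cost is a wording amendment with IRB review. Sample size, data collection and the efficacy analysis do not change.

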5.1 Non-hematological Toxicities

The dose of Pegylated interferon will be reduced for any of the following toxicities at least possibly attributed to Pegylated interferon

- Any Grade 4 non-hematological toxicity
- Any Grade 3 non-hematological toxicity with the specific exclusion of:

- Grade 3 nausea and vomiting controlled by antiemetics
- Grade 3 fever or infection
- Grade 3 fever, myalgias, arthralgias, and rigors.
- Grade 3 hypophosphatemia, hypokalemia, hypocalcemia or hypomagnesemia responsive to oral supplementation.

- Any Grade 2 non-hematologic toxicity that persists for > 3 days and is considered sufficiently medically significant or sufficiently intolerable by patients that it requires treatment interruption
- Any other adverse event attributed to Pegylated interferon that requires treatment interruption for > 3 days or which recurs upon drug re-challenge and requires treatment interruption.
- Non-hematological toxicity that causes a delay of more than 14 days between treatment cycles.

Patients who experience non-hematologic toxicity should have appropriate laboratory testing at least weekly until the toxicity has resolved.

If the toxicity does not return to less or equal than Grade 1 within **14** days, the patient will no longer be eligible to receive treatment on this study.

If the toxicity returns to less or equal to Grade 1 within 14 days, the patient may restart the study drug at initial dose modification once weekly and remain at that dose.

If the same Grade 3 or 4 non-hematologic toxicity recurs, hold drug and wait until toxicity returns to less or equal to Grade 1. If toxicity returns to less or equal to grade 1 within 14 days, the patient may restart the study drug at second dose modification and remain at that dose. If the toxicity does not return to less than Grade 1 within **14** days, the patient will no longer be eligible to receive treatment on this study.

If the same Grade 3 or 4 non-hematological toxicity recurs and it is felt to be due to the study drug, the patient will no longer be eligible to receive pegylated interferon alfa-2b.

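### Section 5.1 gives two restart doses for a child already at the first dose modification who then has a different, or a Grade 2, listed toxicity

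*Combined protocol and SAP*

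**What the plan says.** Section 5.0 sets the general scheme. "Patients who experience significant toxicity as listed in section 5.0 will have the dose reduced by 25% of the dose on subsequent cycles"; two reductions are allowed, and "Patients who again experience dose modifying toxicity after 2 dose reductions will be taken off protocol therapy". Its table describes the first modification as a 25% reduction and the second as a 50% reduction. For the handling of interruptions and modifications it refers the reader to the rules that follow it.

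Section 5.1 opens with a mandatory line: "The dose of Pegylated interferon will be reduced for any of the following toxicities at least possibly attributed to Pegylated interferon". The list beneath covers Grade 4 events, most Grade 3 events, other events that force an interruption, and long delays. It also includes "Any Grade 2 non-hematologic toxicity that persists for > 3 days" where the toxicity is significant or intolerable enough to interrupt treatment.

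The restart text comes next. If the toxicity settles to Grade 1 or less within 14 days, "the patient may restart the study drug at initial dose modification once weekly and remain at that dose". The following paragraph begins "If the same Grade 3 or 4 non-hematologic toxicity recurs, hold drug" and, on resolution within 14 days, says "the patient may restart the study drug at second dose modification and remain at that dose". The closing sentence ends treatment "If the same Grade 3 or 4 non-hematological toxicity recurs and it is felt to be due to the study drug".

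Section 8.1 removes a patient for significant, at least possibly related toxicity despite two reductions. Section 4.4 bars raising the dose again after a reduction for toxicity. Section 9.6 counts a toxic event when a patient has had two reductions and then a further significant toxicity.

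**The concern.** The trigger list in 5.1 is broad, covering any listed toxicity and including some Grade 2 events. The stated step down to the second modification is narrow, requiring the same toxicity at Grade 3 or 4. The restart sentence before it carries no such limit and assigns the initial modification to whatever toxicity has resolved. A clinician with a child already at the first modification, facing a new kind of toxicity, therefore finds one sentence that demands a reduction and another that names the dose the child is already on.

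If the restart sentence is followed, the child resumes at the dose at which the new toxicity occurred. The child may also be recorded as having had one reduction, so that the two reductions needed for a 9.6 toxic event are reached later or not at all.

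**Working it through.** The point is a comparison of texts, and the plan has no figure to reproduce. In each case below the toxicity is on the 5.1 list, is at least possibly related to the drug, and settles to Grade 1 or less within 14 days.

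| Child's situation | Restart text of 5.1, read literally | 5.1 opening line and 5.0 |
|---|---|---|
| On full dose, first listed toxicity | 75% | 75% |
| At 75%, same Grade 3 or 4 toxicity recurs | second modification | second modification |
| At 75%, a different listed toxicity | 75% | second modification |
| At 75%, a listed Grade 2 toxicity, new or recurring | 75% | second modification |
| At 75% because of a 5.2 hematologic toxicity, then a listed 5.1 toxicity | 75% | second modification |
| At the second modification, a different listed toxicity | 75%, an escalation barred by 4.4 | off therapy (5.0, also 8.1) |

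Row 2 takes the last two paragraphs of 5.1 as successive steps, because they share the same literal trigger. Rows 3 to 5 are the conflict. Row 6 shows that the restart sentence cannot have been meant to apply beyond the first reduction, although nothing in it says so.

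**Size of the dose difference.** The 5.0 table does not say which dose its 50% refers to, and the 5.0 text speaks of 25% per reduction. The second step, as a percentage of standard dose, is therefore one of:

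- table applied to the standard dose: 100 − 50 = 50
- table applied to the current dose: 75 × 0.50 = 37.5
- 25% taken off the current dose: 75 × 0.75 = 56.25

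The gaps to 75 are 75 − 50 = 25, 75 − 37.5 = 37.5 and 75 − 56.25 = 18.75 percentage points. All are positive, so the conflict does not depend on how the table is read.

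The standard dose is 1 mcg/kg weekly. For an assumed 40-kg child the restart sentence gives 0.75 × 40 = 30 mcg. The second modification gives 0.50 × 40 = 20 mcg, or 0.375 × 40 = 15 mcg, or 0.5625 × 40 = 22.5 mcg (25 mcg after the rounding up to 5 mcg in 4.3). Before rounding, the difference is proportional to weight, at 0.1875 to 0.375 mcg/kg.

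**Reductions counted.** After two different toxicities the restart sentence leaves the child with one reduction; 5.0 gives two. The first review threshold in 9.6 is 2 events among 9 patients, so one child counted differently is half of the number needed.

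**The case against.** The best defence is that 5.1 never confines the second modification to a recurrence of the same toxicity; it describes one route to it. Read in order, the word initial marks the restart sentence as the first-occurrence step. A child already at 75% then falls under the mandatory opening line and 5.0. That line is an instruction, while the restart sentence is permissive, and restarting at an unchanged dose is not a reduction.

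This is probably what was intended, and row 6 of the table supports it. It does not remove the problem. The restart sentence is not limited to a first occurrence, it covers any resolved toxicity, and 5.0 directs the clinician to these very rules for what to do. The intended reading has to be inferred from outside the sentence that names the dose.

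A reader might go further and infer that 5.1 contradicts 8.1, or keeps on treatment a child who should come off after two reductions. The documents do not support that. The closing sentence of 5.1 is one ground for removal; 5.0 and 8.1 add broader grounds that apply alongside it, and nothing in 5.1 says that such a child stays on. Section 8.1 is also silent on who receives the second modification. The closing sentence is merely narrower than 5.0, and it repeats the trigger of the paragraph before it.

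A reader might also infer a measurable loss in the safety monitoring. The documents give no frequency for this sequence of toxicities, so no probability can be attached.

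**Conclusion.** The concern holds for the restart step. For a child already at the first modification with a different listed toxicity, or a listed Grade 2 one, that resolves within 14 days, 5.1 read literally gives 75% of standard again. Its own opening line and 5.0 require the second modification, which is 18.75 to 37.5 points lower (25 points if the table refers to the standard dose). The number of reductions that 9.6 relies on may also be too low by one for that child.

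The conclusion rests on a literal reading of the restart sentence; sites that follow the opening line and 5.0 will have no difficulty. The consequences are bounded: 9.6 prompts a review and not a stop, 9.8 still summarises individual toxicities and reductions, and 8.1 lets the physician take the child off therapy. It is worth correcting because it concerns which dose to prescribe to a child after toxicity.

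**What to change.** Amend 5.1 in three places:

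- Limit restart at the initial modification to the patient's first dose reduction.
- Replace the same-toxicity, Grade 3 or 4 condition for the second modification with any toxicity on the 5.1 list, same or different, in a patient already at the first modification, whether that reduction was for a 5.1 or a 5.2 toxicity. The second modification follows once the toxicity settles to Grade 1 or less within 14 days.
- For consistency, have the closing sentence refer to the 5.0 rule that any dose-modifying toxicity after two reductions ends protocol therapy.

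Section 5.2 needs no text on the 14-day rule, which belongs to non-hematologic toxicity. At most, add a note that a 5.2 toxicity uses the next 5.0 step. Sections 9.6 and 9.8 need no change on this account.

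The cost is a few sentences by protocol amendment, with no extra patients, visits or procedures. The downside is that some children are reduced sooner than under the literal restart text, which 5.0 already requires.

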5.2 Hematologic Toxicity

The dose of Pegylated interferon will be reduced for any of the following toxicities:

- Grade 4 decreased neutrophil count (neutropenia) > 5 days duration
- Grade 4 decreased platelet count (thrombocytopenia) > 5 days duration
- ≥ 2 platelet transfusions per cycle for platelet counts < 30,000/ μ L
- ≥ 14 day delay in starting subsequent cycles due to low ANC (< 1,000/ μ L or low platelet count (less than 100,000/ μ L.)

Patients who experience hematologic toxicity should have appropriate laboratory testing at least weekly until the toxicity has resolved.

6.0 DRUG INFORMATION

6.1 Pegylated Interferon (Pharmaceutical Information PEG-Intron™ , Other Names: peg-interferon alfa-2b)

Chemical Structure: PEG-INTRON™ is a covalent conjugate of recombinant interferon alfa-2b with polyethylene glycol (PEG). It is derived using recombinant DNA technology on a genetically engineered Escherichia coli bacterium that contains an interferon gene from human leukocytes.

Molecular weight: 31,000 daltons

Manufactured by: Schering-Plough/ MERCK

How supplied: PEG-INTRON™ is a lyophilized powder supplied in 2 ml vials for subcutaneous use. Each vial contains 74 µg, 118.4 µg, 177.6 µg, or 222 µg of PEG-INTRON™, and 1.11 mg dibasic sodium phosphate anhydrous, 1.11 mg monobasic sodium phosphate dihydrate, 59.2 mg sucrose and 0.074 mg polysorbate 80. Following reconstitution with 0.7 ml of supplied diluent (Sterile water for injection, USP), each vial contains PEG-INTRON™ at strengths of 100 µg/ml, 160 µg/ml, 240 µg/ml, or 300 µg/ml, respectively.

SYLATRON:

Manufactured by: Schering-Plough/MERCK

Preparation and Administration

Reconstitute SYLATRON with 0.7 mL of Sterile Water for Injection, USP.

Reconstitution of SYLATRON Single-Use Vials	Diluent (Sterile Water for Injection, USP)	Deliverable Product and Volume	Final Concentration
SYLATRON Single-Use Vial 200 mcg* add	0.7 mL	= 200 mcg in 0.5 mL	40 mcg/0.1 mL
300 mcg† add	0.7 mL	= 300 mcg in 0.5 mL	60 mcg/0.1 mL
600 mcg‡ add	0.7 mL	= 600 mcg in 0.5 mL	120 mcg/0.1 mL

*Total vial content of SYLATRON is 296 mcg.

†Total vial content of SYLATRON is 444 mcg.

‡Total vial content of SYLATRON is 888 mcg.

Swirl gently to dissolve the lyophilized powder. **DO NOT SHAKE.**

- Visually inspect the solution for particulate matter and discoloration prior to administration. Discard if solution is discolored, cloudy, or if particulates are present.
- Do not withdraw more than 0.5 mL of reconstituted solution from each vial.
- Administer SYLATRON subcutaneously. Rotate injection sites.
- If reconstituted solution is not used immediately, store at 2°-8°C (36°-46°F) for no more than 24 hours. Discard reconstituted solution after 24 hours. **DO NOT FREEZE.**

Storage and Stability:

The reconstituted solution should be used immediately and cannot be stored for more than 24 hours at 2-8° C. The reconstituted solution contains no preservative, is clear and colorless. Do not freeze.

Administration: Pegylated interferon will be administered subcutaneously once weekly, on the same day each week. Rotating sites. **Guidelines for administration:**

Education to the parents/patient and or caregivers will be provided on how to measure and draw the adequate amount of medication and subcutaneous administration will be taught to the family. Keep refrigerated. Procedures for proper handling and disposal of hazardous/anticancer drugs should be considered.

Adverse reactions reported with INTERFERON ALFA (Package insert)

CNS: neurologic deficits, headache, decreased mental status, dizziness, impaired memory, impaired concentration, paresthesia, confusion, change in taste or smell, irritability, insomnia, anxiety, change in behavior, visual disturbance, seizures, gait disturbances, hallucinations, encephalopathy, psychomotor retardation, coma, stroke, transient ischemic attacks

Psychiatric: agitation, manic behavior, psychotic reactions, depression, suicidal ideation
Flu-like symptoms: fatigue, myalgia, arthralgia, fever, chills, asthenia, sweating, leg cramps, malaise

Gastrointestinal: nausea, vomiting, diarrhea, anorexia, abdominal pain, flatulence, impaired digestion, gingival bleeding, pancreatitis, colitis, gastrointestinal hemorrhage, stomatitis, abdominal fullness, hypermotility, hepatitis, dysphasia

Skin: injection site reaction, alopecia, hair change, rash, dry skin, pruritus, hematoma, psoriasis, eczema, seborrhea, bruising

Pulmonary: dryness or inflammation of the oropharynx, epistaxis, rhinitis, sinusitis, coughing, dyspnea, pneumonitis

Cardiovascular: rhythm disturbances, chest pain, hypotension, hypertension

Laboratory: neutropenia, thrombocytopenia, anemia, elevated liver function tests, proteinuria.

Other: conjunctivitis, menstrual irregularity, syncope, sexual dysfunction, coagulopathy, weight loss, night sweats, thyroid dysfunction, diabetes

Frequency of Side Effects of Pegylated Interferon

Likely or Common Happens to 21 to 100 children out of every 100	Less Likely or Occasional Happens to 5 to 20 children out of every 100	Rare but Serious, Happens to less than 5 children out of every 100.

 Injection site inflammation and reaction (bruise, itchiness, irritation) flu-like syndrome (headache, malaise, 	
 dry skin pharyngitis impaired concentration confusion dizziness decrease neutrophil decrease in platelet 	
 dry mouth sweating excessively blurred vision/conjunctivitis neuropsychiatric events, including suicide, suicidal and homicidal ideation, depression, aggressive behavior

 fatigue, myalgia) • fever • alopecia • depression • anxiety/emotional lability/irritability • joint pain • nausea/vomiting • muscle pain • insomnia • rigors • irritation of the liver • anorexia/decrease in appetite • 	
counts
 
 • hypothyroidism • hyperthyroidism • Hyperglycemia • abdominal pain • bloody diarrhea • chest pain • weight loss • gingival bleeding • proteinuria • flushing 	
 • psychotic reactions • agitation/nervousness • hypotension, arrhythmia, tachycardia, • cardiomyopathy, angina pectoris, myocardial infarction • Dyspnea, pulmonary infiltrates, pneumonia, bronchiolitis obliterans, interstitial pneumonitis and sarcoidosis • pancreatitis • Development or exacerbation of autoimmune disorders (e.g. thyroiditis, rheumatoid arthritis, interstitial nephritis, systemic lupus erythematosus, psoriasis) • hypersensitivity reactions/allergic reactions • rash • may impair human fertility • menstrual disorder • ischemic colitis
--	--	--

Drug Interactions (Package Insert).

Drugs Metabolized by Cytochrome P-450: When administering Pegylated interferon with medications metabolized by CYP2C8/9 (e.g., warfarin and phenytoin) or CYP2D6 (e.g., ondansetron, flecainide), the therapeutic effect of these substrates may be decreased.

Methadone: Pegylated interferon may increase methadone concentrations. The clinical significance of this finding is unknown; however, patients should be monitored for signs and symptoms of increased narcotic effect.

